2.2. Pooling Algorithm for Analysis Centers

If positive treatment effects are found in a trial with appreciable numbers of subjects per centre, there should generally be an exploration of the heterogeneity of treatment effects across centers, as this may affect the generalizability of the conclusions. As it is expected that for this trial subjects will be recruited over a large number of centers with a small number of subjects per study center, there is no need to check for treatment by center interactions. In addition, the primary endpoint is an objective endpoint, which is evaluated by a central viral monitor, and thus, no heterogeneity across centers is anticipated. Therefore, no pooling algorithm for analysis centers will be specified.

2.3. Analysis sets

The analysis populations covered by this SAP will be:

Randomized Analysis set (RAND): All randomized subjects with a randomization date at or before the date of first intake of medication, or with a randomization date and a missing date for first medication intake.

Safety Set or All Subjects Treated set (AST): All subjects who received at least 1 dose of study drug, analyzed as treated.

Randomized or Treated (RT) set: All subjects who are in the Randomized Analysis Set (RAND) and/or the All Subjects Treated (AST) set.

Intention-To-Treat (ITT) set: All randomized subjects who receive at least 1 dose of study drug. Analyses on the ITT Set will be analyzed as randomized.

Intention-To-Treat-infected (ITT-i) set: All randomly assigned subjects who receive at least 1 dose of study drug and who have an RSV infection confirmed by a PCR-based assay at the central laboratory.

For the interim analysis: a subject is considered to have a confirmed infection with RSV if he/she has been diagnosed with RSV infection based on a PCR-based assay at the local laboratory and for which the RSV infection is confirmed by central laboratory or for which the result of the central laboratory testing is not available at cut-off.

Analyses on the ITT-i Set will be analyzed as randomized.

Per-Protocol (PP) Analysis set: All subjects in the ITT-i set who do not have protocol violations that may have an impact on the efficacy analysis. Decisions regarding which subjects are included in the PP set will be made before database lock on following criteria:

- Compliance: Subjects must have at most 1 missed dose. On the day of randomization at least one dose needs to be taken (so missed dose cannot be the first dose).
- The actual treatment must be the same as the planned treatment.
- No unblinding may have taken place during the study.
- Subjects will be excluded from the PP set if they have taken concomitant medications that may have affected the efficacy of the trial medication. Subjects will be excluded on a case by case basis using a list provided by clinical.
- Subjects may not violate inclusion criteria 3 or 4, nor exclusion criteria 1, 3, 8, 9, 10 or 13.

Analyses on the Per-Protocol set will be analyzed as randomized. Note that in the Per-Protocol set subjects will have been treated as randomized by definition.

The Randomized or Treated Analysis set (RT) will be used in all listings. The Safety set or All Subjects Treated set (AST) will be used to perform the evaluation of all safety variables. The Intention-To-Treat-infected set (ITT-i) will be used to perform the evaluation of all efficacy variables. The Per-Protocol (PP) and Intention-To-Treat (ITT) sets will be used to provide supportive analysis of the primary and selected secondary endpoints only (hospital length of stay, hospital discharge readiness, need for and duration of supplemental oxygen and time to clinical stability, ordinal scale score).

2.4. Statistical Methods

This SAP covers the statistical analysis for the final analysis. The interim analysis and IDMC analysis will be described in separate SAPs. Details of the single displays are described in the Data Presentation Specifications (DPS).

- The analysis population will be indicated in the titles of the displays.
- Unless stated otherwise, all results will be presented per treatment group. Tables on subject disposition, exposure, demographic data and baseline disease characteristics will include a ‘Total’ group, pooling all subjects. Tables on safety will include a “ALS-008176” group.
- Listings will be presented by treatment group and ordered by subject number and time point (if applicable).
- All outputs should be self-explanatory and therefore appropriate footnotes will be provided to clarify the contents of each listing, table or graph.
- In case the X-axis of a graph shows a time component, the distances between the time points will be proportional (not equidistant). Furthermore, when statistics are joined over time by a line, the actual statistics will be depicted by means of a symbol.
- Unless specified otherwise, continuous parameters will be summarized using the following statistics: number of observations, mean, standard deviation, minimum, median and maximum. The mean and median will be presented with one decimal place, while the standard deviation with two decimal places more than the decimal places of the raw data. The minimum and maximum will be presented to the same number of decimal places as the raw data.
- RSV RNA viral load mentioned in this document refers to the RSV RNA viral load qRT-PCR from nasal swab, unless otherwise stated.

2.5. Definition of Subgroups

The following subgroups will be investigated for efficacy (primary and selected secondary endpoints):

Region [Japan, non-Japan]

Age category [≥ 50 to < 65 years and ≥ 65 years]

Sex [Female, Male]

Baseline RSV Viral load [$\leq C \log_{10}$ copies/mL, $> C \log_{10}$ copies/mL] with C = rounded median

Comorbidities [Yes, No]

Use of systemic corticosteroids prior to treatment with ALS-008176 [Yes, No]

Duration of RSV symptoms prior to first treatment [≤ 3 Days; > 3 Days]

Baseline viral subtype [RSV A; RSV B]

Completion of planned study therapy

The following subgroups will be investigated for safety (complete safety for region, selected summary tables for age category, race and BMI):

Region [Japan, non-Japan]

Age category [≥ 50 to < 65 years and ≥ 65 years]

Race [Caucasian, Black, Asian, Other]

BMI [< 25 ; $25 - < 30$; ≥ 30]

Medical review will be done immediately before data base lock on a list with unique coded medical history terms (MedDRA Preferred Terms) to indicate which subjects had comorbidities. The following list of comorbid disease will be identified and potentially analyzed for efficacy (in case at least 15 subjects are enrolled in each of the subgroups):

- Comorbid diseases associated with risk for lower respiratory tract disease^{[1][2]}
 - Asthma [Yes/No]
 - COPD [Yes/No]
 - CHF [Yes/No]
 - CAD (coronary artery disease) [Yes/No]
- Other conditions/therapy of potential interest due to risk of infections in general:
 - Diabetes mellitus [Yes/No]
 - CRF (Chronic Renal Failure) [Yes/No]
 - Use of systemic corticosteroids (PO, IV) prior to or during the treatment phase [Yes/No], based on medical review on a list with unique coded concomitant medications.

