9.9.4. Potential Risks

The nonclinical toxicity profile for ALS-008112 was similar to that previously observed for other marketed nucleoside analogs, where hematopoietic changes and genotoxicity were noted.

The toxicity profile established for ALS-008112 in nonclinical toxicology studies indicates a reversible and dose-related effect on the hematopoietic system where changes in bone marrow cytology were associated with changes in hematological parameters. Specifically, decreased circulating reticulocytes, changes in RBC-related parameters, and hypocellularity of erythroid cell lines in the bone marrow were observed, next to changes on white blood cells, mostly lymphocytes and neutrophils, along with changes in the bone marrow myeloid cells and lymphoid organs. Thrombocytopenia was seen in the dog at very high exposure.

As of 02 January 2018, in adult subjects hospitalized with RSV, 2 hematological serious/severe AEs have occurred and subsequently resolved. In these 2 cases (pancytopenia SAE in Study 64041575RSV2003; severe neutropenia in Study ALS-8176-510), the subject received ALS-008176, but both cases were confounded by multiple medical comorbidities and recent/concomitant use of multiple medications that have been reported to cause bone marrow toxicity. In addition, two Grade 4 SAEs of (febrile) neutropenia (laboratory Grade 4) considered possibly related to the study drug were reported in hospitalized pediatric subjects infected with RSV (1 subject in the MAD part of Study ALS-8176-503 and 1 subject in Study 64041575RSV2004).

Based on the available information, hematopoietic toxicity is considered a potential risk for ALS-008176 for adult and pediatric subjects, for which continued close monitoring of hematological parameters and clinical status in both RSV- and hMPV-infected and healthy subjects is warranted, as additional data are being collected in ongoing/future studies with ALS-008176. Importantly, these hematological side effects observed in both nonclinical and clinical studies with ALS-008176 were reversible.

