10. SUBJECT COMPLETION/DISCONTINUATION OF STUDY TREATMENT/ WITHDRAWAL FROM THE STUDY

10.1. Completion

A subject will be considered to have completed the treatment phase of the study if he or she has completed the treatment regimen and the Day 7 visit or the visit 1 day (+2 days) after the final dose of study drug if the study drug administration is increased to up to 10 days following IDMC review of the data. A subject will be considered to have completed the study if he or she has completed assessments of the last follow-up visit.

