10.2. Discontinuation of Study Treatment/Withdrawal From the Study

Discontinuation of Study Treatment

A subject will not be automatically withdrawn from the study if he or she has to discontinue treatment before the end of the treatment regimen.

A subject's study treatment must be discontinued if:

- The subject withdraws consent.
- The investigator believes that for safety reasons or tolerability reasons (eg, AE) it is in the best interest of the subject to discontinue study treatment.
- The subject becomes pregnant.
- The subject has an eGFR ≤ 30 mL/min/1.73 m² according to the CKD-EPI equation.
- The subject experiences any of the laboratory abnormalities as specified in Section 9.7.1.

If a subject discontinues study drug before the end of the treatment phase, the subject will be encouraged to continue with end-of-treatment and follow-up assessments in accordance with the [Time and Events Schedule](#).

Withdrawal From the Study

Each subject has the right to withdraw at any time for whatever reason without affecting the right to treatment by the investigator. The investigator should make an attempt to contact the subjects who do not return for scheduled visits or follow-up. Although the subjects are not obliged to give reason(s) for withdrawing early, the investigator should make a reasonable effort to ascertain the reason(s) while fully respecting the subject's rights.

A subject will be withdrawn from the study for any of the following reasons:

- Lost to follow-up.
- Withdrawal of consent.
- Death.
- The subject is poorly compliant with study procedures, study drug administration, visits, and assessments, after evaluation and discussion between the investigator and sponsor.

- Decision by the sponsor to stop or cancel the study.
- Decision by the investigator to withdraw subjects.
- Decision by local regulatory authorities and IEC/IRB to stop or cancel the study.

If a subject withdraws from the study before the end of the treatment phase, the subject will be encouraged to continue with end-of-treatment and follow-up assessments in accordance with the [Time and Events Schedule](#).

If a subject is lost to follow-up, every reasonable effort must be made by the investigator/study-site personnel to contact the subject and determine the reason for discontinuation/withdrawal. The measures taken to follow-up must be documented.

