Attachment 7: Visit Schedule for Rash Management for Adult Subjects

This visit schedule summarizes the visits and assessments to be performed in case of rash. At the investigator's discretion, additional visits and assessments can be performed.

	Grade 1 Rash	Grade 2 Rash	Grade 3 or 4 Rash
Day 1 of rash¹	
 Study medication may be continued. Unscheduled visit for initial rash evaluation REQUIRED. Digital pictures REQUIRED (preferably within 24h). Referral to dermatologist (preferably within 24h) ONLY IF rash diagnosis or relationship with study medication is uncertain. 	
 Study medication MUST be permanently DISCONTINUED. Rechallenge is NOT ALLOWED. Unscheduled visit for initial rash evaluation REQUIRED. Digital pictures REQUIRED (preferably within 24h). Referral to dermatologist (preferably within 24h) ONLY IF rash diagnosis or relationship with study medication is uncertain. 	
 Study medication MUST be permanently DISCONTINUED. Rechallenge is NOT ALLOWED. Unscheduled visit for initial rash evaluation REQUIRED. Digital pictures REQUIRED (within 24h). Referral to dermatologist REQUIRED (preferably within 24h). At discretion of the investigator or at request of the dermatologist, assessment of safety blood sample. Biopsy ONLY IF required by dermatologist.
Day 2	
 Follow-up visit REQUIRED.² Digital pictures REQUIRED. 	
 Follow-up visit REQUIRED.² Digital pictures REQUIRED. 	
 Follow-up visit REQUIRED. Digital pictures REQUIRED.
Day 3	No rash follow-up visit required. ²	No rash follow-up visit required. ²	
 Follow-up visit REQUIRED. Digital pictures REQUIRED. At discretion of the investigator or at request of the dermatologist, assessment of safety blood sample.
Day 4	No rash follow-up visit required. ²	No rash follow-up visit required. ²	
 Follow-up visit REQUIRED. Digital pictures REQUIRED. At discretion of the investigator or at request of the dermatologist, assessment of safety blood sample.
Day 5	No rash follow-up visit required. ²	No rash follow-up visit required. ²	
 Follow-up visit REQUIRED. Digital pictures REQUIRED. At discretion of the investigator or at request of the dermatologist, assessment of safety blood sample.

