4.2.3. Primary Efficacy Endpoint

4.2.3.1. Definition

The primary estimates of the AUC will be derived from a mixed model (see section 4.2.3.2 for the detailed specification). No imputations of missing data from nasal swabs post-baseline will be done in this model, as this mixed model would allow to make inferences under the *missing at random* assumption.

Note that for the primary endpoint the following rules apply:

- Only values as provided by the central lab will be used.
- Baseline (Day 1) is defined as the last measurement before first intake. In case a result is available that is no later than 1 hour after treatment initiation this may be used but only if no pre-treatment observation is available.
- If for the baseline assessment the central laboratory value is missing, the value that will be imputed is based on the average value as based on the analysis population (ITT-i, ITT or PP population).
- For all post-baseline days the RSV RNA viral load result of the swab that was performed at that day will be used, counting from the Day of first treatment which is defined as Day 1.
- In case multiple nasal swabs were taken on a single day the average on the log scale will be used as the value for that subject.

As a sensitivity analysis, descriptive statistics will be provided for the viral load AUC calculated by the trapezoidal summation rule, based on planned days of sampling (Baseline visit up till/including Day 7 visit, or up to 11 days if the dose duration is extended to up to 10 days), including the timepoints with (imputed) values available:

$$AUC_{0-7 \text{ days}} = \frac{1}{2} \sum_{i=1}^n (y_i + y_{i-1}) \times (t_i - t_{i-1})$$

where $i=1,2,3,\dots,n$ are the time points when post baseline samples are collected, y_i is the log 10 viral load at the time and t_i is the time in hours post baseline. y_0 is the baseline log 10 viral load. t_0 is time 0.

The following additional rules, on top of the rules of the primary analysis, will be applied to deal with missing values post-baseline before calculating the Viral load AUC:

- Missing value between baseline and day 7 will be imputed by intrapolation.
- If the last observations are missing, the last available observation will be carried forward. Unscheduled assessments will be included and will be eligible for carrying forward.

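### Completion of planned therapy is listed as an efficacy subgroup although it is settled after randomisation, so comparing arms within it is open to selection bias in either direction

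*SAP*

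**What the plan says.** SAP 2.5 opens its first list with "The following subgroups will be investigated for efficacy (primary and selected secondary endpoints". Eight factors on that list are known before the first dose: region, age, sex, baseline viral load, comorbidities, prior systemic corticosteroids, symptom duration and viral subtype. The ninth is "Completion of planned study therapy". It has no levels, no definition, and no caution about interpretation.

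The nearest definition is in Protocol 10.1, where a subject completes the treatment phase if "he or she has completed the treatment regimen and the Day 7 visit" (with a later visit if dosing is extended). The primary endpoint runs from baseline to Day 7 (Protocol 2.1.2). SAP 4.2.3.1 gives the sampling span for its trapezoidal version as "Baseline visit up till/including Day 7 visit".

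Treatment must stop in several situations. Protocol 10.2 includes an eGFR limit and the case where "The subject experiences any of the laboratory abnormalities as specified in Section 9.7.1", meaning the liver and haematology thresholds. For rash of Grade 2 or above, Attachment 7 says "Study medication MUST be permanently DISCONTINUED". Protocol 9.9.4 states that "hematopoietic toxicity is considered a potential risk for ALS-008176 for adult and pediatric subjects".

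The main efficacy analysis does not condition on completion: "The Intention-To-Treat-infected set (ITT-i) will be used to perform the evaluation of all efficacy variables" (SAP 2.3).

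A further list in SAP 2.5, of comorbid conditions and therapies that may be analysed for efficacy, includes systemic corticosteroid use either before or during the treatment phase.

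**The concern.** A subgroup factor fixed at baseline leaves the arms comparable by randomisation within each level. Completion does not. It is observed while the outcome accrues, and both the assigned arm and the severity of illness can influence it. If the subjects who drop out of the completer group differ between arms in their underlying viral AUC, the completer comparison shows a difference that the drug did not cause, or hides one that it did.

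This is a dose-finding trial whose results are meant to inform the design of later studies (Protocol 1.2). If stopping differs by dose, a completer table could colour the view of which regimen performs better. The complementary table of non-completers would be very small. The minimum of 15 subjects per subgroup in SAP 2.5 is attached to the comorbidity list, not to this factor.

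**Working it through.** **Timing.** Under Protocol 10.1, completion is known at the Day 7 visit. Under a narrower reading (all ten doses taken) it is known on Day 5 or 6. Either way it is settled after randomisation and within the AUC window.

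**The plan's own figure.** Neither document gives a figure for this subgroup. The only scale available is the design effect in SAP 1.4: about 90% power at d = 0.77 and about 80% at d = 0.67, with 90 subjects randomised 1:1:1. A simulation took the larger of the plateau and linear contrasts at one-sided 2.5%, with O'Brien-Fleming-type spending and looks at 15, 22 and 30 per arm (timing assumed). It gives 90.7% and 81.1% when both active arms carry the full effect. The stated power reproduces and this point does not change it.

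**Size of a possible shift.** Let p be the share stopping in an arm and D the mean AUC of stoppers minus that of completers, in SD units. The arm mean equals the completer mean plus pD, so the completer mean is the arm mean minus pD. With no drug effect the arm means are equal, and the completer comparison (active minus placebo) is

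shift = -(p_active x D_active - p_placebo x D_placebo).

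The values of p and D are assumptions. Negative values favour active.

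| Stopping, active v placebo | D (active, placebo) | Shift (SD) |
|---|---|---|
| 20% v 10% | 0.5, 0.5 | -(0.20 - 0.10) x 0.5 = -0.05 |
| 20% v 5% | 1, 1 | -(0.20 - 0.05) x 1 = -0.15 |
| 30% v 5% | 1, 1 | -(0.30 - 0.05) x 1 = -0.25 |
| 10% v 10% | 1, 1 | 0 |
| 20% v 5% | 0, 0 | 0 |
| 20% v 5% | -1, 1 | -(-0.20 - 0.05) = +0.25 |

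The middle case, 0.15 SD, is 0.15 / 0.77 = 19% of the design effect. The first and third rows are the ends of the range for 20-30% v 5-10% stopping and D of 0.5 to 1.

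**Second model as a check.** Each subject stops when a latent frailty, correlated rho with AUC, passes a threshold. There is no drug effect. Stopping rates are in the order placebo/low/high.

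- Equal stopping (5% or 10%) with the same mechanism in all arms: bias about 0.
- 5/15/20%: -0.06 SD (rho 0.3) to -0.10 SD (rho 0.5).
- 5/20/30%: -0.09 to -0.16 SD. A nominal one-sided 2.5% test among completers would reject 5.7% to 9.6% of the time.
- Opposite mechanisms (rho +0.3 on placebo, -0.3 on active): +0.06 to +0.18 SD over the rates tried.

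**Non-completers.** At 5% to 30% stopping, an arm of 30 yields 0.05 x 30 = 1.5 to 0.30 x 30 = 9 subjects. That is thin for a six-visit repeated-measures model with unstructured covariance (SAP 4.2.3.2).

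**The case against.** The strongest reply is that nothing confirmatory rests on this line. Efficacy is evaluated on ITT-i, the alpha-controlled contrasts belong to the primary analysis, and subjects who stop drug are encouraged to continue assessments (Protocol 10.2). SAP 2.5 says only that subgroups will be investigated. This stands, and it limits the damage to a supportive table.

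The stopping rules are not viral load criteria. Neither document ties liver, blood count, renal or rash stops to viral AUC, so neither the existence nor the direction of bias is shown. This also stands. The claim has to be that the comparison is open to bias.

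The primary model adjusts for baseline log10 viral load and its interaction with visit. If the subgroup analysis uses that model, whatever part of the stopper difference baseline viral load explains is removed. The figures above are unadjusted and could be too large for that reason.

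The per-protocol set allows at most one missed dose (SAP 2.3) and is also applied to the primary endpoint, so a similar selection would survive deletion of the subgroup. That is correct. But the per-protocol set is defined and labelled supportive, whereas the completion subgroup is undefined and sits beside baseline factors as if it were one of them.

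Finally, defining the levels and labelling the output descriptive would also reduce misreading. It would, but the table adds little that disposition and the per-protocol analysis do not already give.

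**Conclusion.** The point holds as a weakness of a supportive analysis. Completion is a post-randomisation factor that treatment and disease course can influence, so the arms compared within it lose the protection of randomisation. Under the assumed stopping rates and AUC differences, the unadjusted shift for a null drug is 0.05 to 0.25 SD in favour of active, and 0.15 SD at 20% v 5% stopping with a 1 SD difference. It reverses if those who stop on active have lower AUC. It is nil if stopping is unrelated to outcome or selects identically in all arms. The documents supply neither a stopping rate nor a link between stopping and viral AUC, so these figures show scale and are not estimates.

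A reader might infer three stronger things that the documents do not support:

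- **That the completer comparison is biased.** This would need stopping to be related to outcome and to select differently between arms. Both are plausible; neither is shown.
- **That the less well tolerated arm is flattered.** This holds only if those who stop have higher viral AUC. The sign is unknown.
- **That the primary result is at risk.** The ITT-i test, its type 1 error and its power do not depend on this subgroup.

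Corticosteroid use during the treatment phase has the same defect, because it too can follow from treatment and disease course.

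**What to change.** In SAP 2.5, delete completion of planned therapy from the efficacy subgroup list. SAP 4.1.2 already tabulates treatment completion and discontinuation with reasons, and that is where it should be reported.

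In the same section, restrict the corticosteroid factor in the comorbidity and therapy list to use before the first dose. It then matches the prior-use factor in the first list, and the two can be aligned.

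Keep the per-protocol analysis as supportive, and do not present it as a bias-free replacement: it also conditions on compliance after randomisation. If the effect under full treatment is of interest, define completion and pre-specify an estimand with a suitable method.

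The cost is SAP wording and fewer supportive tables. Data collection, sample size and the primary analysis do not change.
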